6.4.2 Blood Chemistry Profile

Blood will be obtained and sent to the clinical site chemistry lab for determination of the following: sodium (Na) potassium (K), chloride (Cl), creatinine, blood urea nitrogen (BUN), aspartate aminotransferase (AST), alanine aminotransferase (ALT), total bilirubin, alkaline phosphatase, glucose, total protein, albumin, calcium, magnesium, phosphorus, lactate dehydrogenase (LDH), amylase, and lipase.

All listed serum chemistries will be performed during screening, D1 of each treatment cycle, and at the end of treatment as outlined in the Time and Events table.

6.4.3 Urinalysis

A standard urinalysis test (Dipstick test) will be obtained at screening and at Cycle 1, and at other times as clinically indicated, as outlined in the Time and Events table below. The analysis includes testing for the presence of proteins, glucose, ketones, hemoglobin, bilirubin, urobilinogen, nitrite, and leucocytes as well as testing of pH and specific gravity.

6.4.4 Endocrine Test

At the screening visit and then repeated on D1 of cycle 4/week 10 visit (section 7.4.4) and D1 of cycle 6/week 16 visit (section 7.4.6): The endocrine test at baseline should include measurement of thyroid stimulating hormone (TSH), free thyroxine 4 (fT4).

During study treatment on D1 of cycles 7, 8 and 9 scheduled at weeks 19, 22, 25, respectively, and also at the end of study visit: the endocrine test will only need to include TSH and fT4.

6.4.5 Pregnancy Test

A pregnancy test (β -hCG) will be obtained from female subjects who are of childbearing age prior to their participation in the study. A negative urine pregnancy test must be performed within 3 days prior to receiving the first dose of study drug i.e., within 72 hours of administration of the first dose of entinostat.

6.5 Correlative Studies

6.5.1 Collection of Peripheral Blood Mononuclear Cells (PBMC)

Peripheral blood (approximately 50 mL at each time point) will be collected for isolation of PBMCs using the Ficoll isolation technique for multiparameter flow cytometry (immunoregulatory subsets and assessment of H3 and H4 acetylation levels).

Samples will be collected at baseline; in the end of cycle 1, beginning of cycle 2 (day 22±2 days), immediately before concurrent entinostat-pembrolizumab; week 10; and end of treatment (i.e., at time of withdrawal for progression or other reasons) D105/wk16 visits, as outlined in the Time and Events table in Section 7.1.

6.5.2 Mandatory On-Treatment Biopsy

A mandatory (excisional, punch or CT-guided) biopsy will be obtained in the end of cycle 1, beginning of cycle 2 (day 22±2 days), immediately before concurrent entinostat-pembrolizumab treatment.

6.5.3 Targeted panel somatic mutation sequencing

If this has not been previously done as part of patient's standard of care, archived tumor tissue will be submitted to Foundation Medicine (foundationmedicine.com) for FoundationOne® testing. FoundationOne® assesses somatic mutations across 300 cancer-associated genes, computes tumor mutation burden, assesses expression of PD-L1, and calculates tumor infiltrating lymphocyte density, as per standard of care. If patient's tumor has been previously submitted for targeted panel sequencing using other commercially available tests these tests would be acceptable on condition that sequencing has been performed on >100 genes and that all exomes of these genes have been sequenced (i.e. not just hotspot mutations). Results from other non-FoundationOne targeted sequencing panels will be at the discretion of the principal Investigator. Results are not required to be available at the time of initiation of study treatment.

7.0 EVALUATIONS AND ASSESSMENTS

7.1 Time and Events Table

Assessments ¹	Pre-screening	Screening ¹ D-21→-0	Study Treatment ³							End of Tx ⁴ ±7d	Long-term follow up ⁴
			D1 Wk1	D22 Wk4	D43 Wk7	D64 Wk10	D85 Wk13	D106 Wk16	D127, D148, D169 Wks19, 22, 25		
			D1 Cycle 1	D1 Cycle 2	D1 Cycle 3	D1 Cycle 4	D1 Cycle 5	D1 Cycle 6	D1 Cycles 7, 8, 9		
Informed Consent ²	X	X									
History, PE		X	X	X	X	X	X	X	X	X	X
Serum/Urine Pregnancy Test		X	X								
ECOG PS		X	X	X	X	X	X	X	X	X	
Concomitant Meds		X	X	X	X	X	X	X	X	X	
Hematology		X	X	X	X	X	X	X	X	X	
Serum Chemistry		X	X	X	X	X	X	X	X	X	
Endocrine tests		X				X		X	X ⁵	X	
Coagulation tests ⁵		X									
Urinalysis ⁶		X	X								
12-lead ECG		X		X		X		X	X	X	
Toxicity Assessment		X	X	X	X	X	X	X	X	X	
Brain MRI		X								X	
Whole body CT		X				X		X	X ⁸	X	
Patient pill diary (entinostat)			X	X	X	X	X	X	X	X	
Entinostat ⁷			X	X	X	X	X	X	X ⁸		
Pembrolizumab ⁷				X	X	X	X	X	X ⁸	X ⁹	
Blood for isolation of PBMCs			X	X		X				X	
Archival tissue assessment ¹⁰	X										
Fresh Tumor Biopsy				X ¹¹							
FoundationOne®		X									

(Note: Week 1 includes days 1-7; week 2 includes days 8-14; week 3 includes days 15-21, etc.)

Key to Footnotes

1. All screening assessments should be obtained within 21 days before initiating study treatment, unless specified below:
 - a. Screening labs obtained within 72 hours of D1 of study treatment do not need to be repeated on D1/cycle 1 visit.
 - b. The serum pregnancy test should be obtained during screening and a urine pregnancy test should be obtained within 72 hours before starting entinostat treatment on D1/cycle 1.
2. Informed consent at pre-screening visit in order to access archival tissue or perform fresh tissue biopsy if archival tissue is unavailable or insufficient, to confirm unresectable stage III or distant metastatic disease. Main consent is to be signed at the screening visit.
3. Study Treatment assessments:
 - a. All study treatment visits should be performed within (± 1) day for the first two weeks of study therapy.
 - b. For the cycle 1/day 2 visit (i.e., Study Day 22) visit the window is ± 2 days,
 - c. Then ± 3 days for assessments scheduled on D1 of cycles 3 and 4 and then ± 7 days for assessments scheduled on D1 of all subsequent cycles.
4.
 - a. Refer to section 7.5.1 for guidance on end of study treatment requirements for this study.
 - b. Refer to section 7.5.2 for guidance on long-term follow up requirements for this study.
5. Perform coagulation tests at screening, as described in section 4.1.9. Perform at other visits if necessary per discretion of the investigator.
6. Urinalysis at screening, at Cycle 1, and other times as clinically indicated.
7. Entinostat and pembrolizumab should be dosed as outlined in Sections 5.2 and 5.2.1.
8. Following radiographic disease assessment on week 16, patients will be seen by the investigator every 21 days for AE review and initiation of a new treatment cycle (i.e., every 3 weeks starting on D1 of weeks 19, 22, and 25 (see section 7.4.7) and at the end of study treatment visit (see Section 7.5.1) for details of scheduled assessments. Radiographic disease assessment will occur at D1 of cycle 8 during this period.
9. Following completion of the trial treatment (i.e., 9 cycles of protocol-directed therapy) at 28 weeks, pembrolizumab dosing may be continued per investigator discretion on condition that there is no disease progression and patient continues to receive clinical benefit. Treatment will be administered as per standard of care guidelines off study.
10. If archival tissue is unavailable or insufficient, fresh biopsy should be performed in order to confirm unresectable stage III or distant metastatic disease.
11. The biopsy should be performed at the end of cycle 1, beginning of cycle 2 (day 22 ± 2 days), immediately before concurrent entinostat-pembrolizumab treatment.

7.2 Pre-Screening Assessments

1. Pre-screening informed consent,
2. Pathology assessment for eligibility,

7.3 Screening Assessments

3. Informed consent,
4. Clinical evaluation: complete history and complete physical exam,
5. ECOG performance status,
6. Concomitant medication review,
7. Toxicity/safety assessment,
8. Brain MRI (or CT scan with IV contrast, if applicable),
9. Whole body CT (chest, abdomen and pelvis; neck if applicable). MRI of the abdomen/pelvis with IV contrast can be an acceptable equivalent, if clinically indicated
10. 12-lead ECG,
11. Targeted panel sequencing (FoundationOne®), if it has not previously performed. Results are not required to be available at the time of study drug initiation. If patient's tumor has been previously submitted for targeted panel sequencing using other commercially available tests these tests would be acceptable on condition that sequencing has been performed on >100 genes and that all exomes of these genes have been sequenced (i.e. not just hotspot mutations). Results from other non-FoundationOne targeted sequencing panels will be at the discretion of the principal Investigator.
12. Laboratory studies:
 - Pregnancy Test
 - Hematology
 - Serum Chemistries
 - Urinalysis
 - Endocrine test (screening visit)

7.4 Study Treatment Assessments

7.4.1 Study Day 1 ± 1 day (D1 of Cycle 1/Week 1)

1. Clinical evaluation: focused history and physical exam,
2. ECOG performance status,
3. Laboratory studies: (*do not repeat if pre-study assessments performed within 72 hours of this visit)
 - Hematology*
 - Serum Chemistries*
 - Urinalysis, including urine pregnancy test (as clinically indicated)*
 - Collect peripheral blood for isolation of PBMCs (approximately 50 mL)
4. Concomitant medication review,
5. Toxicity/Safety Assessment,
6. Patient pill diary review and patient training on diary instructions.

7. Entinostat self-administration with study staff present. **One 5 mg tablet is to be dosed weekly; dispense 2 additional 5-mg tablets for D8 and D15 home administration.

7.4.2 Study Day 22 ± 2 days (D1 of Cycle 2/Week 4)

1. Clinical evaluation: focused history and physical exam,
2. ECOG performance status,
3. 12-lead ECG,
4. Laboratory studies:
 - Hematology
 - Serum Chemistries
 - Collect peripheral blood for isolation of PBMCs (approximately 50 mL)
5. Mandatory Fresh Tumor biopsy (excisional, punch, or CT-guided),
6. Concomitant medication review,
7. Toxicity Assessment,
8. Patient pill diary check,
9. Entinostat administration: 5mg PO to be administered after mandatory biopsy; also dispense two 5-mg pills for administration on D28 and D35,
10. Pembrolizumab administration: 200 mg IV dose; to be administered after mandatory biopsy and after entinostat intake.

7.4.3 Study Day 43 ± 3 days (D1 of Cycle 3/Week 7)

1. Clinical evaluation: focused history and physical exam,
2. ECOG performance status,
3. Laboratory studies:
 - Hematology
 - Serum Chemistries
4. Concomitant medication review,
5. Toxicity Assessment,
6. Check Patient pill diary,
7. Entinostat administration in clinic and additional doses taken on cycle day 8 and cycle d15
8. Pembrolizumab administration: 200 mg IV dose; to be administered after entinostat intake.

7.4.4 Study Day 64 ± 7 days (D1 of Cycle 4/Week 10)

1. Clinical evaluation: focused history and physical exam,
2. ECOG performance status,
3. 12-lead ECG,
4. Laboratory studies:
 - Hematology
 - Serum Chemistries
 - Endocrine panel: fT4/TSH
 - Collect peripheral blood for isolation of PBMCs and plasma (approximately 50 mL)
5. Concomitant medication review,
6. Toxicity/safety Assessment,

7. Disease assessment: whole body CT (chest, abdomen and pelvis; neck if applicable),
8. Entinostat administration: in clinic and additional doses taken on cycle day 8 and cycle d15,
9. Pembrolizumab administration: 200 mg IV dose; to be administered after entinostat intake.

7.4.5 Study Day 85 ± 7 days (D1 of Cycle 5/Week 13)

1. Clinical evaluation: focused history and physical exam,
2. ECOG performance status,
3. Laboratory studies:
 - Hematology
 - Serum Chemistries
4. Concomitant medication review,
5. Toxicity Assessment,
6. Patient pill diary check,
7. Entinostat administration: in clinic and additional doses taken on cycle day 8 and cycle d15,
8. Pembrolizumab administration: 200 mg IV dose; to be administered after entinostat intake.

7.4.6 Study Day 106 ± 7 days (D1 of Cycle 6/Week 16)

1. Clinical evaluation: focused history and physical exam,
2. ECOG performance status,
3. 12-lead ECG
4. Laboratory studies:
 - Hematology
 - Serum Chemistries
 - Endocrine panel: ft4/TSH
5. Concomitant medication review,
6. Toxicity Assessment/safety,
7. Disease assessment (chest, abdomen and pelvis; neck if applicable),
8. Patient pill diary check,
9. Entinostat administration: in clinic and additional doses on cycle day 8 and cycle d15,
10. Pembrolizumab administration: 200 mg IV dose; to be administered after entinostat intake.

7.4.7 Study Days 127, 148, 169 (D1 of Cycles 7, 8 and 9/Wks 19, 22, 25) (within ± 7 days for each visit)*

*Visits on pembrolizumab dosing infusion day 1 of wks 19, 22 and 25

1. Clinical evaluation: focused history and physical exam,
2. ECOG performance status,
3. 12-lead ECG on cycle 8
4. Laboratory studies:
 - Hematology
 - Serum Chemistries
 - Endocrine panel: ft4/TSH only
5. Concomitant medication review,
6. Toxicity/safety assessment,

7. Disease assessment: D1 of Cycle 8 (chest, abdomen and pelvis; neck if applicable),
8. Patient pill diary check,
9. Entinostat administration: in clinic and additional doses taken on cycle day 8 and cycle d15 before pembrolizumab on weeks 19, 22, and 25
10. Pembrolizumab administration: 200 mg IV dose; to be administered after entinostat intake on weeks 19, 22, and 25

7.5 Post Treatment Follow-Up Assessments

7.5.1 End of Study Treatment Visit (Week 28, or earlier if disease progression, intolerable toxicity, patient withdraw) within + 7 days of stopping study treatment

1. Clinical evaluation: focused history and physical exam,
2. ECOG performance status,
3. 12-lead ECG
4. Laboratory studies:
 - Hematology
 - Serum Chemistries
 - Endocrine panel: include fT4/TSH only
5. Disease assessment (chest, abdomen and pelvis; neck if applicable),
6. Collect peripheral blood for isolation of PBMCs and plasma (approximately 50 mL)
7. Brain MRI (if applicable),
8. Concomitant medication review,
9. Toxicity Assessment.

7.5.2 Long Term Follow-up Assessments

Patients who have not progressed on pembrolizumab plus entinostat after 27 weeks of treatment will be followed every 3 months (+/- 15 days) for up to 2 years post study treatment with phone calls or standard of care visits. The following information will be recorded:

- (a) details regarding systemic treatment for their melanoma that they are currently on (type, response if any, duration on treatment, treatment-related side effects),
- (b) whether they have progressed (and when) from current PD-1 inhibitor treatment,
- (c) whether treatment-related AEs that patients may have developed during the year of entinostat-pembrolizumab treatment have resolved, and when,
- (d) whether they are alive or not; if dead, precise date of death.

Patients who progressed on pembrolizumab plus entinostat before completing 27 weeks of study therapy will be followed every 3 months (+/- 15 days) for up to 2 years since study initiation with phone calls or standard of care visits. The following information will be recorded:

- (a) systemic treatment for their melanoma they are currently on (type, response if any, duration on treatment, treatment-related side effects),
- (b) whether treatment-related AEs that patients may have developed during the year of entinostat-pembrolizumab treatment have resolved, and when,
- (c) whether they are alive or not; if dead, precise date of death.

Patients removed from study treatment for unacceptable AEs will be followed for resolution or stabilization of the adverse event(s). Following resolution of adverse events they will be followed every 3 months (+/- 15 days) for up to 2 years since study initiation with phone calls or standard of care visits. All patients (including those withdrawn for AEs) should be followed after removal from study treatment as stipulated in the protocol.

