5.9 Duration of Follow Up

Patients who have not progressed on pembrolizumab plus entinostat after 27 weeks of treatment will be followed every 3 months (\pm 2 weeks) for up to 2 years following treatment initiation (C1D1). Follow ups include phone calls or visits. The following information will be recorded: (a) details regarding systemic treatment for their melanoma that they are currently on (type, response if any, duration on treatment), (b) whether they have progressed (and when) from current PD-1 inhibitor treatment, (c) whether treatment-related AEs that patients may have developed during the 27 weeks of entinostat-pembrolizumab treatment have resolved, and when, (d) whether they are alive or not; if dead, precise date of death.

Patients who have progressed on pembrolizumab plus entinostat within the 27 weeks of the study duration will be followed every 3 months (\pm 2 weeks) for up to 2 years following treatment initiation. Follow up may include phone calls or visits. The following information will be recorded: (a) systemic treatment for their melanoma they are currently on (type, response if any, duration on systemic anticancer treatments, systemic anticancer treatment-related grade 2 or higher AEs), (b) whether treatment-related AEs that patients may have developed during the year of entinostat-pembrolizumab treatment have resolved, and when, (c) whether they are alive or not; if dead, precise date of death.

Patients removed from study treatment for unacceptable AEs will be followed for resolution or stabilization of the adverse event(s). All patients (including those withdrawn for AEs) should be followed after removal from study treatment as stipulated in the protocol.

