9.1.1 Definitions

Evaluable patients are those who complete all activities by at least day 22, namely: (a) they have received at least one and up to 4 entinostat weekly doses on day 1 and day 8, 15 and 22 (b) they have received the first pembrolizumab infusion on day 22 (± 2 days), and (c) they have completed day 22 (± 2 days) mandatory tumor biopsy. The rationale for this is to answer the primary translational endpoint regarding entinostat-alone immunomodulatory effects in peripheral blood and tumor tissue with sufficient power.

- SAE are events that meet FDA's definition as defined in [section 8.1.4](#) of the protocol irrespective of attribution to study drug(s). Subjects who receive at least one dose of entinostat are evaluable for safety.

- ORR by RECIST 1.1 criteria is the sum of complete response and partial response.

- PFS is measured from the date of enrollment on study to the date of documented progression. The rate of patients who are progression-free will be specifically calculated at 27-weeks (approximately 6 months) from study entry.

- OS is measured from the date of enrollment on study to the recorded date of death. The rate of patients who are alive at 27-week (approximately 6 months) will be specifically calculated for the study.

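### Follow-up after a toxicity stop lists no progression item and PFS has no censoring rule, so 27-week status can be unknown for these patients

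*Combined protocol and SAP*

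**What the plan says.** Section 7.5.2 describes three follow-up groups.

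- **Not progressed at the end of the treatment period.** "Patients who have not progressed on pembrolizumab plus entinostat after 27 weeks of treatment will be followed every 3 months". One listed item is "whether they have progressed (and when) from current PD-1 inhibitor treatment".
- **Progressed before completing 27 weeks.** Later therapy, resolution of AEs and survival are listed.
- **Stopped for toxicity.** "Patients removed from study treatment for unacceptable AEs will be followed for resolution or stabilization" of the event. The section continues: "Following resolution of adverse events they will be followed every 3 months", for up to 2 years. No items are listed for this group: not progression, not new therapy, not survival.

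Section 5.9 has the same structure, but does not give the toxicity group even the 3-monthly schedule. It closes with a general statement: "All patients (including those withdrawn for AEs) should be followed after removal from study treatment as stipulated in the protocol".

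On imaging, section 7.5.1 gives patients who stop for intolerable toxicity an end-of-treatment visit with one disease assessment, within 7 days of stopping. The long-term follow-up column of the table in section 7.1 shows history and physical examination but no CT.

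On analysis, section 9.1.1 states: "The rate of patients who are progression-free will be specifically calculated at 27-weeks". Section 9.3 says that PFS will be estimated by Kaplan-Meier. Neither section says how a toxicity stop, a new therapy or a missing scan is handled.

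**The concern.** The 27-week PFS rate is secondary objective 2.2.2 and endpoint 3.2.2. It needs each patient's progression status at about week 27. A patient who stops for toxicity at week 12, say, without progression, has not had 27 weeks of treatment and so does not fit the group for whom progression is recorded. That patient may also no longer be on the PD-1 inhibitor treatment to which the progression item refers. Sites that follow the text exactly could collect nothing on progression after the end-of-treatment scan.

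Such exits are possible by design. Section 5.3.2 requires permanent discontinuation of pembrolizumab for several immune-related events, and entinostat must then stop as well. Section 5.5 places no restriction on therapy after treatment ends, so what these patients receive next may also change their risk of progression.

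If such patients are censored at their last scan, Kaplan-Meier assumes that their later risk equals that of patients still under observation. In a trial of 10 to 14 patients, one or two of them shift the estimate visibly. Data that were never collected cannot be recovered at analysis.

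**Working it through.** **1. The plan's own figures.** No figure is stated for PFS. The only operating characteristics, in section 9.2, belong to the primary rule of at least 3 conversions in 10. The exact binomial formula is 1 − Σ C(10,x) pˣ(1−p)¹⁰⁻ˣ for x = 0 to 2. It gives 0.0401 at p = 0.08 and 0.8327 at p = 0.4, against the stated 0.04 and 83%. The figures reproduce. They rest on the day-22 biopsy, so the point made here does not touch them.

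**2. Does another section fill the gap?**
- Section 5.1 gives restaging at week 10 and then every 6 weeks until week 27, without tying it to treatment.
- Section 9.1 ties the same assessments to pembrolizumab treatment.
- Section 5.1(b) counts toxicity patients as having completed all trial requirements if samples and tumor assessments are complete by at least week 3. That is before the first restaging at week 10.
- The general sentence in 5.9 defers to what the protocol stipulates, and for this group no items are stipulated.

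On balance, no scan after the end-of-treatment visit is clearly required.

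**3. Timing of contacts.** Three months is about 13 weeks. If the clock starts at AE resolution, resolution after week 27 − 13 = 14 puts the first contact after week 27. With the 15-day window used to the full, the cut-off is about week 16.

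**4. How much is left undetermined.** With n patients and k toxicity stops of unknown week-27 status, the rate lies between s/n and (s + k)/n, where s is the number known to be progression-free. The width is k/n. The documents give no toxicity-stop rate, so k = 1 to 4 is an assumed range. Its upper end is taken from section 5.10, which warns about more than 4 withdrawals.

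| n | k = 1 | k = 2 | k = 3 | k = 4 |
|---|---|---|---|---|
| 10 | 10 points | 20 | 30 | 40 |
| 14 | 7 points | 14 | 21 | 29 |

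**5. Illustration (assumed data).** Of 10 patients, 2 progress at week 10, 2 stop for toxicity at week 12 and are censored, 1 progresses at week 16 and 1 at week 22.
- Kaplan-Meier: (8/10) × (5/6) × (4/5) = 0.533.
- Both toxicity stops progressed by week 27: 4/10 = 0.40.
- Neither progressed: 6/10 = 0.60.
- Simple proportion with the two dropped: 4/8 = 0.50.

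**6. Direction of bias (assumed inputs).** Take exponential PFS with a 27-week rate of 40% on the on-treatment hazard, a constant hazard of toxicity stop with probability p by week 27, and a hazard multiplied by h after stopping. Let L = −ln 0.4 = 0.916 and M = −ln(1 − p). The true rate is

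e^−(L+M) + M·e^−hL·[1 − e^−(M+L−hL)]/(M + L − hL).

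For p = 0.2 and h = 2, M = 0.223 and the rate is 0.320 + 0.223 × 0.16 × 1.443 = 0.372. Kaplan-Meier with censoring at the stop tends to 0.40.

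| h | p = 0.1 | p = 0.2 | p = 0.3 |
|---|---|---|---|
| 0.5 | 41.1% | 42.2% | 43.4% |
| 1 | 40% | 40% | 40% |
| 2 | 38.6% | 37.2% | 35.6% |
| 3 | 37.7% | 35.6% | 33.2% |

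Against 40%, Kaplan-Meier is pessimistic by 1.1 to 3.4 points at h = 0.5, unbiased at h = 1, and optimistic by 1.4 to 4.4 points at h = 2 and by 2.3 to 6.8 points at h = 3.

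**The case against.** A reader might infer that progression is not collected at all after a toxicity stop, and that the PFS rate is therefore biased upward. The documents do not support either step.

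- **Collection is unspecified, not excluded.** There is an end-of-treatment scan and there are 3-monthly contacts for up to 2 years. Section 5.10 asks patients who withdraw to allow record abstraction for long-term objectives. A careful site could capture progression. This stands as a correction to the stronger reading. It does not close the gap, because nothing tells the site to do so, and the example given in 5.10 is survival.
- **No censoring rule is written.** Censoring at the last scan is inferred from the naming of Kaplan-Meier. The wording in 9.1.1 could also mean a simple proportion. That is true, but a proportion needs the same missing status.
- **Direction is unknown.** Whether censoring is informative depends on the hazard after stopping, which the documents do not give. The bias is zero if that hazard is unchanged and reverses if it falls.
- **Frequency is unknown.** Section 5.3.3 reports that the combination was well tolerated, section 5.3.2 allows restarting after many events, and the 20% in section 9.2 pools toxicity with screen failure and rapid progression. It cannot be said how many such exits to expect.
- **Nothing is decided on PFS.** There is no threshold or hypothesis for it, and section 1.1 calls the secondary endpoints exploratory. Sampling error is also large: the exact 95% interval for 4/10 is about 0.12 to 0.74. This limits the seriousness. However, a confidence interval does not cover uncertainty from missing status, and that part is avoidable.

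**Conclusion.** The gap holds. For patients who stop for toxicity before progression and before week 27, the plan specifies one end-of-treatment disease assessment. After that come contacts with no listed content, no scheduled imaging and no PFS censoring rule. Their 27-week status can be unknown, which risks informative censoring of secondary endpoint 3.2.2.

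The firm part of the size is k/n: 10 percentage points per unknown patient at n = 10, and 7 at n = 14. The bias figures depend on assumed toxicity-stop rates and hazards, and they run in either direction. The primary endpoint, its decision rule and its operating characteristics are unaffected. This should be corrected because the data cannot be recovered later, but it does not threaten the trial's main conclusion.

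**What to change.** **Sections 5.9 and 7.5.2.** For every patient off treatment without progression, whatever the reason, record at the 3-monthly contacts:
- progression, with its date and basis, from standard-of-care imaging;
- the start of any new systemic therapy;
- survival status.

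Count the contacts from treatment stop rather than from AE resolution, and include a status at week 27.

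**Section 9.3.** Count documented progression or death up to week 27 as an event. State how patients with no imaging, or with new therapy before progression, are handled. Whether progression after a new therapy counts is a choice of estimand, and the plan should make it explicitly. Report best-case and worst-case 27-week rates for patients of unknown status. Align section 9.1.1 with section 3.2.2 at the same time: 3.2.2 starts PFS at day 1 of treatment and includes death, while 9.1.1 starts at enrollment and names only progression.

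**Cost.** This is a cheap improvement: a few more data items at largely existing contacts, and some analysis wording. No scans are mandated. The downside is that off-treatment scan dates will be less regular, so progression dates for these patients will be less exact.
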